Homeless adults receiving treatment at Metrocare at the Bridge will be given a flyer that briefly outlines this study. Interested individuals will be scheduled for a screening visit to determine study eligibility. We may give participants a card to remind them of their appointment time. Prior to screening, potential participants will receive information about this voluntary study and will be informed that Bridge and Metrocare services are not contingent upon study enrollment. Interested participants will sign a consent form prior to completing the screener. The screener includes questions about demographics, alcohol use, use of technology, and other questions.

We will notify subjects in real-time whether or not they are eligible to be in the study and can proceed with the baseline survey. Eligible participants will complete a separate consent form and then complete the in-person baseline assessments as described below. On the baseline they will provide identifiers that will be linked to the screener information. We will retain screening data for both eligible and ineligible participants.

Participants

Participants will be eligible if they: 1) receive a score of 8 or above on the AUDIT (a measure of alcohol dependence); 2) report consuming at least 1 drink of alcohol in the past week; 3) are receiving treatment at Metrocare; 4) are willing and able to complete the baseline and follow-up visits; 5) score ≥ 4 on the REALM-SF indicating > 6 th grade English literacy level (i.e., a 7th grade reading level is necessary to complete assessments; 12% to 14% of those screened for Projects Advance and Aspire had REALM scores < 7 th grade reading level; <1% of Bridge guests are non-English speakers), and 6) score ≥ 24 on the Mini-Mental State Exam indicating no substantial cognitive impairment. Individuals will be excluded from participating if they indicate on the screener that they would be uncomfortable wearing an alcohol sensing bracelet for 4 weeks (Phase I only). Individuals will be excluded from participating in Phase III if they participated in Phase I.

Individuals who meet the study inclusion criteria and provide informed consent will complete the baseline assessment and 4-week follow-up assessments in a space that is set aside at the Bridge specifically for this study. All participants will receive a smartphone and SCRAM at the first equipment visit, returning the devices at the end of the 4-week period.

In-person Assessments

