In-person assessments will be administered at the baseline and 4-week visits. The surveys will ask about demographics, social network, experiences with homelessness, stress/victimization, social support, mood, health, quality of life and substance use. Some of the questions are asked to evaluate the effect of the intervention (e.g., alcohol, consequences, satisfaction); other questions are asked to determine whether there are factors that moderate (e.g., self-rated mental/physical health diagnosis, stress, status, religious participation) or mediate (e.g., sleep, stress, coping) the effects of the intervention. The locator form and homelessness timeline follow-back will be administered at baseline only. Data will be collected on laptop/tablet computers using Questionnaire Development System (QDS) software. QDS utilizes a computer-administered self-interview format where each item appears on the computer screen while the program simultaneously reads the item (participants use a mouse or touch screen to

Table 1. In person assessment measures.

Background/History
Locator Form
Demographic Information Questionnaire*
Subjective Social Status ¹⁰²
Brief Homelessness Questionnaire
Homelessness Timeline Follow-Back ^{103*}
Health/Mental Health
SF-12 ¹¹⁰
Health Related Quality of Life ¹¹¹
Self-Rated Health
Tobacco Questionnaire
Inadequate Sleep
Time Line Follow-Back ¹¹² (past month alcohol)
Short Inventory of Consequences ¹¹³
Stress/Affect
Personal Victimization ¹⁰⁴
Perceived Stress Scale – Short Version ¹⁰⁵
Urban Life Stress Scale
Depression ¹⁰⁸
Interpersonal/Intrapersonal
Interpersonal Support Evaluation List
Brief COPE
Religious Participation
Treatment Satisfaction
EMI Satisfaction Survey **

*Baseline only

**Follow-up only

select answers only after QDS reads each item). Participants wear headphones so that others do not hear the survey items. Staff will be available to help participants who may have difficulty. We estimate that the baseline visit will take approximately 1 to 2 hours to complete, and the follow-up visit will take approximately 50 to 80 minutes to complete.

Equipment Visits

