Event Sampling will be available to participants on demand. Participants will be instructed to click the “Record Drink” button if/when they have their first drink of a day. Drinking assessments will include all items from the random assessments and will query about the reinforcing value of the drink(s) and causes of the drinking episode.

Geolocation. Consistent with previous work,^{19,20,51} smartphones will collect geo-location coordinates about every 5 minutes. The aim of this study is to identify psychological, social, and contextual variables that predict drinking and heavy drinking days. Previous studies have found that continuous “breadcrumb” tracking can be used to identify important health risk factors.^{19,20,58} We will remove all personal information from the phone once it is returned to us.

Alcohol Sensor

Biosensors can provide a continuous estimate of blood alcohol concentration (BAC) based on the concentration of alcohol in perspiration on the skin.⁵²⁻⁵⁹ The device with the most extensive evaluation is the SCRAM bracelet (Alcohol Monitoring Systems, Littleton, CO), which is worn on the ankle. In Phase I, all participants will wear the SCRAM for 4 weeks. SCRAM has an electrochemical sensor that samples the vapor near the skin every 30 minutes for ethanol, and stores readings for later retrieval. Data from the SCRAM is downloaded to a computer via USB cable, using a 16-digit key and password-protected software. The SCRAM is water resistant and cannot be removed without cutting the strap. The SCRAM system provides alerts if the bracelet sensors detect an obstruction or other tampering. At the 2-week equipment check-in, our staff will review participant readings and any alerts and will address any malfunction or evidence of tampering. To mitigate any potential risk to subjects while wearing the SCRAM monitor:

- a. Law enforcement officers cannot obtain the information even if subjects are taken to jail. SCRAM data are encrypted and need to be connected to the research computer in order to download the data.
- b. The Certificate of Confidentiality (COC) protects investigators from having to disclose SCRAM data to law enforcement or anyone else.
- c. Subjects can cover up the ankle monitor with their clothes and always decline participating in the study.
- d. Subjects will be informed through the consent form that the SCRAM ankle bracelet may draw unwanted attention by law enforcement (and possibly others) to them.

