A brief questionnaire will assess the initial feasibility and acceptability of the app. Specifically, in a final follow-up visit after participating in the EMA, participants will report on the helpfulness of the app and if the number of prompts on the app were appropriate. We will use statistical tests to determine if participants found the app to be helpful and if they would recommend it to others.

Effectiveness of App (Phase III only)

We will compare Phase III participants (i.e., those who received Metrocare, EMAs, and the app features including tailored treatment messages) to Phase I participants (i.e., those who received Metrocare and EMAs only) to examine the preliminary effectiveness of the app. Specifically, we will compare Phase I and Phase III participants' percent drinking days (PDD) and percent heavy drinking days (PHDD; ≥ 5 drinks for men; ≥ 4 drinks for women) using appropriate generalized linear models. We will consider the study phase as the parameter of interest estimating the treatment effect, adjusting for relevant covariates (e.g., gender, race, baseline AUD severity).

Phase I and Phase III

EMA data will be measured repeatedly and are thus correlated within subjects. Thus, our analytic approach will include generalized linear mixed model regression analysis (GLMM), a flexible analytic approach with wide use in health sciences research.¹³⁴ GLMM can handle fixed and random effect model parameters, nested designs, and repeated measures with various correlation structures.^{135,136} GLMM can also handle normal and non-normal outcomes such as dichotomous alcohol use variables, different variance functions, as well as unbalanced designs where the number of observations varies across individuals. Examples of planned GLMM analyses include: 1) testing if random assessments of alcohol urges or measures of affect (each aggregated to one rating per day) predict daily drinking status after controlling for relevant covariates (e.g., gender, race/ethnicity, depression), 2) testing if protective factors (e.g., social support, positive interpersonal interactions, prosocial location) predict alcohol use, and 3) examine trends of number of drinks and drinking days over time, accounting for dependencies of within-person repeated measures.

In addition, EMA data will allow us to examine other important questions like: 1) agreement

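### Bracelet discomfort bars entry to Phase I but not to Phase III, so the compared groups enter under different rules; the bias is of unknown size and direction and can be only partly checked

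*Combined protocol and SAP*

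**What the plan says.** **Entry.** Section C, Participants, excludes people who report on the screener that they would be "uncomfortable wearing an alcohol sensing bracelet for 4 weeks (Phase I only"). Phase III has no matching exclusion. It has a different one: former Phase I participants cannot enter.

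**Comparison.** Section D, Effectiveness of App, compares Phase III (n=40) with Phase I (n=80) on PDD and PHDD: "We will consider the study phase as the parameter of interest estimating the treatment effect", "adjusting for relevant covariates (e.g., gender, race, baseline AUD severity"). Bracelet comfort is not among the examples, and no sensitivity analysis is described.

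**Data at hand.** Section C, Screening Procedures, outlines the screener only: "The screener includes questions about demographics, alcohol use, use of technology, and other questions". Nothing says whether the bracelet item is asked in Phase III. The same subsection adds: "We will retain screening data for both eligible and ineligible participants". Section C, In-person Assessments, states: "In-person assessments will be administered at the baseline and 4-week visits". Table 1 lists the Time Line Follow-Back ("past month alcohol") with neither the baseline-only nor the follow-up-only mark, so it is collected at both visits.

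**Who wears the bracelet.** One sentence in Participants gives a SCRAM to every participant. The exclusion in the same subsection and the Equipment Visits text limit it to Phase I, and Background and Alcohol Sensor describe it for Phase I.

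**The concern.** Unwillingness to wear a continuous alcohol monitor could be related to drinking, and drinking is the outcome. If so, Phase III contains a kind of participant that Phase I screened out, and the phase coefficient mixes that difference with any effect of the app. The named covariates do not clearly cover it. At stake is how far the preliminary-effectiveness estimate can be read as an app effect.

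**Working it through.** The documents state no effect size, SD, power or discomfort rate, so there is no figure to reproduce. Only the group sizes (80 and 40) come from the protocol. Every other input is an assumption, shown over a range.

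**1. Size of the bias.** Let f be the share of Phase III who would be uncomfortable and d their difference in PDD. Unadjusted bias = f × d, of either sign.
- Low: 0.05 × 5 = 0.25 points
- Middle: 0.175 × 17.5 = 3.06 points
- High: 0.30 × 30 = 9 points

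**2. Against sampling noise.** SE = SD × √(1/80 + 1/40) = 0.194 × SD, giving 3.87, 5.81 and 7.75 points at SD 20, 30 and 40. The middle bias is 3.06/SE = 0.79, 0.53 and 0.40 SE. The high corner is 9/3.87 = 2.3 SE down to 9/7.75 = 1.2 SE, so it is not negligible there.

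**3. As a false-positive rate.** With no app effect, a two-sided 5% test and d of 0.2 to 0.8 SD, the rejection rate is 1 − Φ(1.96 − fd/0.194) + Φ(−1.96 − fd/0.194):

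| f | shift fd (SD) | rejection rate |
|---|---|---|
| 10% | 0.02 to 0.08 | 5 to 7% |
| 20% | 0.04 to 0.16 | 6 to 13% |
| 30% | 0.06 to 0.24 | 6 to 24% |

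**4. What baseline drinking can absorb.** If it carries a quarter, half or three quarters of the difference, 3.06 falls to 2.3, 1.5 or 0.8 points. A baseline–outcome correlation r multiplies the SE by √(1 − r²): 0.95, 0.87 and 0.71 at r = 0.3, 0.5 and 0.7. That is relative to a model with no baseline drinking covariate. The planned model already has baseline AUD severity, so the gain over it is unknown.

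**5. What restricting Phase III can show.** With u uncomfortable and c comfortable among the 40, the change from the full to the restricted estimate has 95% half-width 1.96 × (u/40) × √(1/u + 1/c). For u = 7, c = 33: 1.96 × 0.175 × √(1/7 + 1/33) = 0.143 SD, or 2.9, 4.3 and 5.7 points at SD 20, 30 and 40. Against an assumed bias of 3.1 points, the check separates it from zero only at SD 20, and barely. The cost in precision is √[(1/80 + 1/n) / (1/80 + 1/40)] = 1.02, 1.07 and 1.13 for n = 38, 33 and 28 retained.

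**6. Errors in the answer.** Assume sensitivity 70% and specificity 90%. Among those who pass the item, the uncomfortable share is 0.175 × 0.3 / (0.175 × 0.3 + 0.825 × 0.9) = 0.0525/0.795 = 6.6%.
- Only Phase III answers err, and baseline drinking carries half: restriction leaves 8.75 × 0.066 = 0.58 of 1.53 points.
- Both phases err equally: Phase I also holds 6.6%, the unadjusted bias is (0.175 − 0.066) × 17.5 = 1.9 points, and restriction leaves about zero.

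**7. What the screening records can show.** If all other eligible people enrol, Phase I bracelet exclusions number 80f/(1 − f): about 4, 17 and 34 at f = 5%, 17.5% and 30%. The 95% half-width of an AUDIT difference from the 80 enrolled is 1.96 × √(1/80 + 1/k) = 1.00, 0.52 and 0.40 SD. No outcome data are described for these people.

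**The case against.** The rule has a plain operational reason: only Phase I is described as fitting the bracelet, and barring Phase III volunteers over a device they will not wear would shrink a 40-person pilot for nothing. Discomfort may also have little to do with drinking, since the Alcohol Sensor subsection itself warns that "the SCRAM ankle bracelet may draw unwanted attention by law enforcement". The covariate list is open, so baseline drinking could already be intended. All of this stands as mitigation. None of it makes the entry rules equal or plans a check.

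A reader might infer that one cheap sensitivity analysis would show whether the rule matters. The documents do not support that. The Phase III item is not known to be asked, and the expected precision is too low to settle the question. Restriction also does not equalise entry: in Phase I, bracelet-averse people can drop out at the flyer, at either consent step, or by declining after the warning, without ever failing the item.

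A reader might also infer that naming Time Line Follow-Back drinking would cut the SE by 5 to 29% compared with the plan. That range is measured against a model the plan does not propose.

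**Conclusion.** The concern holds in limited form. The compared groups enter under different rules, and nothing planned examines the consequence. The size and direction of any bias cannot be derived from the documents. On mid-range assumptions it is below one SE and probably small against sampling noise; it becomes material only if the uncomfortable share and their drinking difference are both large. The text does not support the reading that the bias is known to favour the app or to count against it, or that the rule by itself invalidates the comparison.

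This is one of several differences tied to phase. Bracelet wear, the zero-BAC check (introduced for the bracelet, with its Phase III use unstated), the bar on former Phase I participants, and calendar time would all remain after any restriction. The contrast would still not be a pure app effect.

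**What to change.** 1. **Covariate.** Name baseline past-month Time Line Follow-Back PDD/PHDD in the phase comparison, in addition to baseline AUD severity. No new data are needed; one SAP sentence.
2. **Comfort item, if Phase III screening is not complete.** Ask it in the Phase I wording, exclude no one, and report its frequency. Beside the all-40 comparison, give an estimate limited to Phase III participants who would have passed, with the interval for the change between the two. Describe it as a partial check that applies to bracelet-comfortable people. Cost: one screener item, one SAP sentence, and a restricted SE about 2 to 13% larger if 5 to 30% are uncomfortable. App Testing says the app content needs IRB approval before Phase III testing, so the item could go in that submission. The document does not state whether Phase III has begun.
3. **Screening table.** From the retained data, report how many people were excluded from Phase I only for bracelet discomfort, with their AUDIT and past-week drinking beside those of the enrolled. This is coarse and misses people who left before the item, but it works whatever the status of Phase III.
4. **Interpretation.** State in the SAP that the other differences listed above remain tied to phase.
5. **Separate wording correction.** Reconcile the Participants sentence that gives every participant a SCRAM with the Phase I limits in Participants and Equipment Visits and the Phase I descriptions in Background and Alcohol Sensor.

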Relatively little is known about the environmental, cognitive, and behavioral antecedents of alcohol use in homeless adults. Like other subgroups, alcohol use has most often been examined using traditional lab/clinic based assessment methods that are not well suited to capturing the complicated street-level interactions experienced by most homeless adults.^{14,15} Ecological momentary assessment (EMA), in which handheld devices (e.g., smartphones) are used to capture moment-to-moment experience, is currently the most accurate way to measure phenomena in natural settings.^{14,16-18} Additionally, recent technological advances have made it possible to collect continuous geolocation data alongside EMA. Researchers can now link environmental risks and protective factors to outcomes, without reliance on subjective reporting alone.^{19,20}

This study will develop and test a “just-in-time” adaptive intervention to reduce alcohol use among homeless adults. During Phase I, we will use smartphones and passive sensing to monitor geolocation, psychosocial variables (e.g., stress, urge to drink), and alcohol use in a group of 80 homeless adults enrolled in shelter-based treatment. In Phase II, we will use this information to create a risk algorithm and tailored treatment messages that anticipate and intervene to prevent alcohol use (there are no human subjects in Phase II). We will modify an existing app, previously validated for smoking cessation, to create the intervention. In Phase III, we will pilot test the newly developed app for utility, satisfaction, and preliminary effectiveness in a group of 40 homeless adults enrolled in shelter-based treatment. In Phase I, alcohol consumption will be validated via a transdermal alcohol sensor (i.e., SCRAM) worn by all participants. If effective, this smartphone app could significantly improve treatment engagement, drinking outcomes, and quality of life among homeless adults with AUDs.

Figure 1. Phase I and III Flowcharts

Phase I (n=80)

Phase III (n=40)

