Approximately 2-3 days after the baseline assessment, participants will receive the cellphone (including instructions on how to complete the phone assessments), and will be fitted with the SCRAM bracelet (Phase I only). In order for the SCRAM to function properly, we will breathalyze participants at this equipment visit to ensure a zero BAC. Participants who do not register a zero BAC will be asked to come back later (or another day if BAC is very high) at a time when it is estimated to be zero. We will review the functioning of both devices, and participants will sign a form indicating that they understand how to care for the devices. Additionally, participants will be asked to complete an equipment visit at 2 weeks (the mid-point of the study period) to verify that the phone and SCRAM are working properly. At the 2-week visit, people can receive payment for the phone assessments they have completed thus far. There are no research assessments at the equipment visits.

Phone Procedures

A Samsung Galaxy Core Prime smartphone (or equivalent) will be loaned to each participant so that they may complete EMAs. Participants navigate through the EMA program and enter data by touching their response on the screen. Participants will be able to call (e.g., if they have problems completing EMAs) and receive calls from research staff through the smartphone free of charge. During their participation in the study:

- a. Subjects are not responsible for any costs related to the cell phone (e.g., lost, stolen, damaged and/or data overages).
- b. Phone services (data & phone package) will be terminated if the phone is lost or stolen, or once the subject completes the intervention.
- c. One replacement will be provided in the event the phone is lost, stolen or damaged.
- d. Subjects can charge their phones at the Bridge, or in any other local establishments.

Phone Assessments

Smart Phone Training. Participants will receive hands-on training on study phone use and will watch a brief step-by-step video tutorial (created by the researchers) at the first equipment visit that demonstrates use of the study phone and app features. This video will also be preloaded onto the home screen of study phones. We have achieved high EMA compliance rates (i.e., 82% of all EMAs completed) using this protocol in a sample of homeless adults.^{23,121}

Three types of EMAs will be used: daily diary, random

Table 2. EMA measures.

Daily Diary
Sleeping Arrangements

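### The Phase I comparator is described without the SCRAM sensor that all its participants wear; if the sensor is Phase I only, the phase coefficient cannot isolate the app

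*Combined protocol and SAP*

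**What the plan says.** In Section D, Effectiveness of App, Phase III is compared with "Phase I participants (i.e., those who received Metrocare and EMAs only) to examine the preliminary effectiveness of the app". Phase III is described as Metrocare and EMA plus the app features, and SCRAM appears in neither description. The outcomes are PDD and PHDD, analysed with generalized linear models. Of the model the SAP says: "We will consider the study phase as the parameter of interest estimating the treatment effect". Gender, race and baseline AUD severity are given as example covariates.

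On the sensor in Phase I, Section B says: "In Phase I, alcohol consumption will be validated via a transdermal alcohol sensor (i.e., SCRAM) worn by all participants". Section C, Alcohol Sensor, agrees: "In Phase I, all participants will wear the SCRAM for 4 weeks". Section C, Equipment Visits, says participants "will be fitted with the SCRAM bracelet (Phase I only", a parenthesis that limits fitting to that phase. Section C, Participants, likewise applies the exclusion for discomfort with the bracelet to Phase I alone.

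Three places mention SCRAM with no phase limit:
- a sentence in Section C, Participants, that gives every participant both a phone and a SCRAM;
- the 2-week equipment check in Section C, which verifies both devices;
- the planned analysis of agreement between SCRAM, Time Line Follow-Back and EMA, which stands in Section D under a heading naming both phases.

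**The concern.** The preliminary-effectiveness part of Aim 3 rests on one coefficient. Its meaning depends on what the two groups received, and the SAP's account of one group leaves out a component. The sensor is not a trivial one: it is strapped on for 4 weeks, cannot be removed without cutting the strap, gives tamper alerts, and has its readings reviewed with staff involvement at 2 weeks. If only Phase I wears it, the contrast is app without sensor against sensor without app. A report that follows Section D would then describe the control condition inaccurately and could credit or debit the app with a difference that belongs to the package. The feasibility and acceptability parts of Aim 3 are not affected.

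**Working it through.** The plan gives no alpha, SD, effect size or power calculation for this comparison, so there is no figure to reproduce. The check is mainly a reconciliation of text, followed by an illustration.

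**1. What each group receives**

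| Reading | Phase I | Phase III |
|---|---|---|
| Section D as written | Metrocare, EMA | Metrocare, EMA, app |
| SCRAM in Phase I only | Metrocare, EMA, SCRAM | Metrocare, EMA, app |
| SCRAM in both phases | Metrocare, EMA, SCRAM | Metrocare, EMA, app, SCRAM |

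Section D matches neither of the two readings that Sections B and C allow. The statements in Section B and under Alcohol Sensor say that Phase I wears SCRAM; they do not say that Phase III does not. That step rests on the parenthesis under Equipment Visits, with the Phase I-only exclusion as indirect support.

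**2. Identifiability if SCRAM is Phase I only**

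Let P = 1 for Phase III and 0 for Phase I. Then app = P and sensor = 1 − P, so app + sensor = 1 for every participant. With an intercept in the model the two effects cannot both be estimated, whatever covariates are added. If the app lowers PDD by a points and the sensor lowers it by s points, the Phase III minus Phase I difference contains −a + s. A positive s therefore understates the app's benefit.

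**3. Calendar period**

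Phase III follows Phase I, because the risk algorithm uses variables identified in Phase I. Enrolment is expected to take about 9 months in Phase I and 6 in Phase III (Section C, Setting), so calendar date varies within each phase. A phase step can be estimated beside a time trend, but only under an assumed form for that trend.

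**4. What baseline data can do**

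"In-person assessments will be administered at the baseline and 4-week visits", and Table 1 includes a Time Line Follow-Back marked "past month alcohol". The devices come later: "Approximately 2-3 days after the baseline assessment, participants will receive the cellphone". Baseline PDD and PHDD are therefore available and precede the sensor. Adjusting for them addresses baseline imbalance, including some of any selection caused by the bracelet exclusion, and improves precision. It cannot remove an effect of wearing the sensor afterwards.

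**5. Illustration (SD, shift and correlation are assumptions)**

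Inputs from the documents: 80 and 40 participants. Assumed: SD of PDD 25, 30 or 35 points, two-sided 5%, no dropout, app with no effect, net sensor shift b.

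SE = SD × √(1/80 + 1/40) = SD × 0.1936

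P(reject) = [1 − Φ(1.96 − b/SE)] + Φ(−1.96 − b/SE)

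| SD | SE | b = 2 | b = 5 | b = 10 |
|---|---|---|---|---|
| 25 | 4.84 | 7.0% | 17.8% | 54.2% |
| 30 | 5.81 | 6.4% | 13.8% | 40.6% |
| 35 | 6.78 | 6.0% | 11.4% | 31.4% |

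With baseline adjustment at an assumed correlation of 0.5 and SD 30, SE = 5.81 × √(1 − 0.5²) = 5.03, and the rates are 6.8%, 16.9% and 51.1%. The adjustment sharpens the estimate but leaves the shift in place.

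The rates are two-sided but not symmetric. At SD 30, unadjusted, b = 10 splits into 40.6% in the direction of the shift and 0.01% against it. If the sensor lowers Phase I drinking, the 40.6% are results against the app.

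**The case against.** **The comparator wording can be read more mildly.** EMA is the route by which the app delivers its messages, so the phrase may mean only that Phase I had no app features. In-person surveys and geolocation are not listed either. This explains the wording. It does not supply the missing component, and since EMA is itself an assessment, the list is not confined to treatments.

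**SCRAM may be worn in both phases.** Three places support this, and if they govern, the sensor difference disappears. That stands as a reason to make the sensor conclusion conditional. The group descriptions would still be incomplete, and the Phase I-only exclusion would remain.

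**The aim is only preliminary, and the comparison across phases is openly stated.** This limits how firm a conclusion may be. It does not change what the coefficient estimates or correct the description of the comparator.

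**The covariate list is open.** This is true, and it already names baseline AUD severity. Baseline PDD and PHDD could be added within the plan as it stands, but they are not named.

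**Stronger readings that the documents do not support.** A reader might infer that the app estimate is biased. Nothing in the documents shows that SCRAM changes drinking, or in which direction. A reader might also infer that calendar period is as inseparable from the app as sensor wear is. It is not, because dates vary within each phase, although separating it needs an assumed trend.

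**Conclusion.** The concern holds in two parts. First, on any reading, the Phase I group is incompletely described in Section D; confidence in this is high, as it rests on direct statements in Sections B and C. Second, if SCRAM is Phase I only, the phase coefficient is a difference between two packages in sequential, non-randomised cohorts, and the app's own effect on PDD and PHDD is not identified. That part depends on the Equipment Visits limit governing over the three unrestricted mentions, which is the better-supported reading but not a settled one.

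The size is unknown. On the assumed values, a 2-point shift hardly matters (6% to 7% rejection against a nominal 5%), while a 10-point shift gives 31% to 54% across SDs of 35 to 25. These are illustrations, not estimates. If monitoring reduces drinking, the error would understate the app's benefit. The matter should be fixed, but it does not undermine the pilot's other aims.

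**What to change.** 1. Reconcile Section C (Participants, Equipment Visits, Alcohol Sensor) and the agreement analysis in Section D, so that they state consistently which phases wear SCRAM. This comes first, because the next step depends on it.
2. Then correct Section D, Effectiveness of App. If SCRAM is Phase I only, describe the comparator as Metrocare, EMA and SCRAM, and state that the phase coefficient is a preliminary difference between packages in sequential, non-randomised cohorts, not the effect of the app alone. If SCRAM is worn in both phases, add it to both group descriptions and keep the caveat on sequential, non-randomised cohorts.
3. On either reading, name baseline PDD and baseline PHDD, from the past-month Time Line Follow-Back, as covariates for the respective outcomes. Report the number excluded for bracelet discomfort from the screening data, which are retained for ineligible people too.

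The cost is wording in Sections C and D, one covariate per outcome from data already collected, and one count. The downside is a more modest effectiveness conclusion. Step 3 helps with baseline imbalance and precision; it does not recover the app effect if the sensor is Phase I only.
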